12. DISCONTINUATION FROM FOLLOW-UP

If a patient withdraws from further follow-up a trial deviation form should be submitted to ICR-CTSU stating whether the patient simply no longer wishes to attend trial follow up visits or whether the patient has withdrawn consent for any further information to be sent to the ICR-CTSU.

Should a patient withdraw consent for their samples to be used in c-TRAK TN, blood samples will be destroyed and tissue samples returned to the site for archiving following receipt of written confirmation from the site to ICR-CTSU.

13. PROCEDURE AT DISEASE RECURRENCE

Disease recurrence should be reported to ICR-CTSU on the appropriate eCRF and confirmed in writing via email ([contact]) as soon as possible. Patients should be treated as per local guidelines for metastatic disease/recurrence. Prior to commencement of any treatment for metastatic disease/recurrence, a ctDNA blood sample should be collected. In addition, a recurrence tumour tissue sample should be provided for each patient who has tissue available from a biopsy taken routinely as part of standard patient care (see section 13.2). Following this no further blood samples for ctDNA analysis should be collected and no further follow up is required.

For patients being treated with pembrolizumab, there is the possibility of development of lymphadenopathy that may not be indicative of disease recurrence. See below for guidance on continuing pembrolizumab treatment.

13.1. Development of lymphadenopathy on pembrolizumab treatment

Immunotherapeutic agents such as pembrolizumab may produce anti-tumour effects by potentiating endogenous cancer-specific immune responses. Immunotherapeutic agents may also induce lymphadenopathy. In addition, response patterns seen with such an approach may extend beyond the typical time course of responses seen with cytotoxic agents, and can manifest as a clinical response after an initial increase in tumour burden or even the appearance of new lesions.

If new lymphadenopathy develops on treatment, staging imaging should be conducted to examine for evidence of disease recurrence according to local guidelines. If there is radiographic evidence of isolated lymphadenopathy patients should remain on treatment if they are clinically stable as defined by the following criteria:

- 1. Absence of signs and symptoms (including worsening of laboratory values) indicating disease recurrence
- 2. No decline in ECOG performance status
- 3. Absence of potential recurrent disease in sites other than lymphadenopathy

Repeat imaging should be done \geq 4 weeks later. If lymphadenopathy remains isolated and has not progressed the patient may continue on pembrolizumab. If lymphadenopathy has progressed, or the patient has developed alternative potential sites of disease, appropriate investigations should be conducted to determine if recurrence has occurred. If recurrence is subsequently confirmed the patient must stop pembrolizumab.

The decision to continue pembrolizumab after first radiologic evidence of isolated lymphadenopathy is at the

investigator's discretion based on the clinical status of the patient.

13.2. Sample collection following recurrence

13.2.1. **Tumour tissue**

A recurrence tumour tissue sample should be provided for each patient who has tissue available from a biopsy taken routinely as part of standard patient care. The tissue sample should be sent to the c-TRAK TN central laboratory as soon as it is available. DNA will be extracted for mutation analysis and comparison with the primary tumour.

13.2.2. ctDNA blood sample

ctDNA blood samples should be provided prior to the patient commencing treatment for the recurrence. 20ml (2 x 10ml) blood should be obtained and send to the c-TRAK TN central laboratory.

14. LIFE STYLE GUIDELINES

Female participants must be surgically sterile or be post-menopausal, or must agree to use effective contraception from registration until 120 days after the last dose of pembrolizumab.

Male participants must be surgically sterile or must agree to use effective contraception after starting the first dose of pembrolizumab through 120 days after the last dose of pembrolizumab.

Accepted methods of contraception are defined in Appendix 2.

15. PARTICIPATION IN OTHER CLINICAL TRIALS

Patients previously entered into a therapeutic trial during or after neoadjuvant chemotherapy are only eligible if no experimental therapy is continued post-surgery. Patients involved in clinical trials involving experimental drugs prior to primary standard treatment (i.e. window of opportunity trials) can be considered for entry into c-TRAK TN. Patients who enter a window of opportunity study after completion of standard chemotherapy may not be eligible, due the potential of the window study treatment to effect ctDNA surveillance in c-TRAK TN. Entry of such patients into c-TRAK TN will be considered on a case by case basis by the TMG.

c-TRAK TN patients will not be permitted to participate in any other trials of investigational medicinal products until completion of follow-up at the time of disease recurrence.

16. c-TRAK TN SCREENING LOG

All participating sites will be required to keep a log of all patients with early stage triple negative breast cancer receiving neoadjuvant chemotherapy and those with confirmed moderate/high risk disease that are potentially eligible for this trial. The information collected on the log will include:

- Date patient identified
- Screening outcome (patient approached/accepted participation/declined participation)

- Reasons for not approaching patient / patient declining participation (if available)
- Registration number (if applicable)

This information will be used by the TMG to monitor recruitment activity. No patient identifiable data should be sent to ICR-CTSU.

17. TRIAL TREATMENT

Pembrolizumab is the investigational medicinal product within c-TRAK TN and is being used outside the licensed indication and will be given as a fixed dose regimen which differs to the standard dose recommended for pembrolizumab. A fixed dose regimen of pembrolizumab is now standard in ongoing pembrolizumab trials. Patients who become ctDNA positive within 12 months of starting ctDNA analysis will be allocated to pembrolizumab treatment.

Prior to the implementation of protocol v6.0 during the randomised component of the trial, patients who become ctDNA positive within 12 months of starting ctDNA analysis were randomised to treatment with pembrolizumab or observation (on a 2:1 ratio).

In protocol version 6.0 randomisation within the trial was removed, all patients with a positive ctDNA result will be allocated to treatment intervention. Any patients already in the observation group, will transition to the non-randomised trial component following re-consent, and be allocated to pembrolizumab at the time of the next positive ctDNA result.

17.1. Dose and schedule

Pembrolizumab will be given at a dose of 200mg as a 30 minute IV infusion (infusion window -5 to +10 minutes) on day 1 of each 3 week cycle. Pembrolizumab should be administered after all pre-treatment assessments have been completed (see section 11.1). Treatment may be administered up to 72 hours before or after the scheduled day 1 of each cycle. Refer to the c-TRAK TN Pharmacy Guidance Notes for specific instructions for the preparation of the pembrolizumab infusion fluid and administration of infusion solution.

17.2. Prescription and dispensing

Pembrolizumab will be supplied in non-patient-specific vials for use within the c-TRAK TN trial only. Pembrolizumab should be labelled, stored and dispensed in accordance with the c-TRAK TN Pharmacy Guidance Notes.

17.3. Patient cards

Small wallet sized cards will be produced by ICR-CTSU on request by the recruiting site. Each card will state:

- the name of the recruiting site
- that the patient is participating in the c-TRAK TN trial
- that the patient is taking pembrolizumab (where applicable)
- an emergency contact number at site

17.4. Duration of treatment

Treatment will continue for a maximum of 12 months. Patients may withdraw from pembrolizumab before this time if they experience unacceptable toxicities or their Principal Investigator (or designated investigator) believes further treatment is no longer appropriate or if the patient withdraws consent for any reason.

17.5. Supportive care

Patients should receive appropriate supportive care measures as deemed necessary by the Principal Investigator (or designated investigator). Suggested supportive care measures for the management of adverse events (AEs) with potential immunologic aetiology are outlined below. Where appropriate, these guidelines include the use of oral or intravenous corticosteroids, as well as additional anti-inflammatory agents if symptoms do not improve with administration of corticosteroids. Note that several courses of steroid tapering may be necessary as symptoms may worsen when the steroid dose is decreased. For each AE, attempts should be made to rule out other causes such as bacterial or viral infection, which might require additional supportive care. The treatment guidelines are intended to be applied when the investigator determines the events to be related to pembrolizumab. It may be necessary to perform conditional procedures, such as bronchoscopy, endoscopy, or skin photography, as part of the AE evaluation.

17.6. Immune-mediated adverse reactions

Immune-mediated adverse reactions occur in patients treated with pembrolizumab. Most adverse reactions are reversible and managed with interruptions of pembrolizumab, administration of corticosteroids and/or supportive care.

For suspected immune-mediated adverse reactions, ensure adequate evaluation to confirm aetiology or exclude other causes. Based on the severity of the reaction withhold pembrolizumab and administer corticosteroids as per guidelines in the table in section 17.16. Upon improvement to grade 1 or less, initiate corticosteroid taper and continue to taper over at least 1 month. Restart pembrolizumab if the adverse reaction remains grade 1 or less. If another episode of a severe adverse reaction occurs, permanently discontinue pembrolizumab.

Centres should monitor signs or symptoms that might indicate development of these adverse reactions and treat as per the guidance in section 17.16.

Treatment with pembrolizumab may increase the risk of solid organ transplant rejection. Patients who have had a solid organ transplant are excluded from c-TRAK TN.

17.7. Management of infusion reactions

Severe infusion reactions, including hypersensitivity and anaphylaxis have been reported in patients receiving pembrolizumab.

Signs and symptoms usually develop during or shortly after drug infusion and generally resolve completely within 24 hours of completion of infusion. Monitor for signs and symptoms including rigors, chills, wheezing, pruritus, flushing, rash, hypotension, hypoxaemia and fever.

Table 2 below shows treatment guidelines for patients who experience an infusion reaction associated with administration of pembrolizumab.

Table 1. Treatment guidelines for infusion reaction associated with administration of pembrolizumab

NCI CTCAE v4.0 Grade	Treatment	Premedication at subsequent dosing
Grade 1 Mild reaction; infusion interruption not indicated; intervention not indicated	Increase monitoring of vital signs as medically indicated until the patient is deemed medically stable in the opinion of the investigator	None
Grade 2 Requires infusion interruption but responds promptly to symptomatic treatment (e.g., oxygen, IV fluids, antihistamines, non- steroidal anti- inflammatory drugs); prophylactic medications indicated for ≤ 24 hours	Stop Infusion and monitor symptoms. Additional appropriate medical therapy may include but is not limited to: Oxygen, IV fluids, antihistamines, non- steroidal anti-inflammatory drugs Increase monitoring of vital signs as medically indicated until the patient is deemed medically stable in the opinion of the investigator. If symptoms resolve within one hour of stopping drug infusion, the infusion may be restarted at 50% of the original infusion rate (e.g., from 100 mL/hr to 50 mL/hr). Otherwise dosing will be held until symptoms resolve and the patient should be pre-medicated for the next scheduled dose. Patients who develop grade 2 toxicity despite adequate premedication should be permanently discontinued from further pembrolizumab administration.	Patient may be pre- medicated 1.5 hours (± 30 min) prior to infusion of pembrolizumab with: Chloraphenamine 10mg po Paracetamol 500-1000mg po
Grades 3 or 4 Grade 3: Prolonged (i.e. not rapidly responsive to symptomatic medication and/or brief interruption of infusion); recurrence of symptoms following initial improvement; hospitalization indicated for other clinical sequelae (e.g. renal impairment, pulmonary infiltrates) Grade 4: Life- threatening; pressor or	 Stop infusion. Additional appropriate medical therapy may include but is not limited to: IV fluids, antihistamines, corticosteroids, oxygen, adrenaline. Increase monitoring of vital signs as medically indicated until the patient is deemed medically stable in the opinion of the investigator. Hospitalization may be indicated. Patient should be permanently discontinued from further pembrolizumab administration. 	No subsequent dosing

NCI CTCAE v4.0 Grade	Treatment	Premedication at subsequent dosing	
ventilatory support indicated			
Appropriate resuscitation equipment should be available in the room and a physician readily available during the period of drug administration.			

17.8. Common adverse reactions related to pembrolizumab

The most serious adverse reactions reported in patients treated with pembrolizumab are immune-related reactions and severe infusion-related reactions (see sections 17.6/17.7). The adverse reactions listed in the table below are common, occurring in at least 1 out of 100 patients treated with pembrolizumab and the majority of those reported were grade 1 or 2 severity. Most reactions are reversible and managed without interruption of pembrolizumab. For the most up to date information on anticipated adverse reactions and their frequency, please refer to the latest version of the pembrolizumab Investigator Brochure

Table 2: Very common d	and common adverse	reactions to pembrolizumab
------------------------	--------------------	----------------------------

System Organ Class	Very Common and Common Adverse Reaction
Blood and Lymphatic system disorders	Anaemia
Endocrine disorders	Hyperthyroidism, hypothyroidism
Gastrointestinal disorders	Diarrhoea, nausea, colitis, vomiting, abdominal pain, constipation, dry mouth
General disorders and administration site conditions	Fatigue, asthenia, oedema, pyrexia, influenza-like illness, chills
Immune system disorders	Infusion related reactions
Investigations	Raised ALT, AST, ALP, creatinine
Metabolism and nutritional disorders	Decreased appetite
Musculoskeletal and connective tissue disorders	Arthralgia, myositis, musculoskeletal pain, pain in extremity, arthritis
Nervous system disorders	Headache, dizziness, dysgeusia
Respiratory, thoracic and mediastinal disorders	Pneumonitis, dyspnea, cough
Skin and subcutaneous tissue disorders	Rash, pruritus, severe skin reactions, vitiligo, dry skin, erythema

17.9. Significant rare reactions related to pembrolizumab

There are some rare adverse events that have been reported in patients treated with pembrolizumab. They occur in <1 in every 100 patients. For the most up to date information on anticipated adverse reactions and their frequency, please refer to the latest version of the pembrolizumab Investigator Brochure.

System Organ Class	Rare Adverse Reaction
Blood and Lymphatic system disorders	Neutropenia, lymphopenia
Musculoskeletal and connective tissue disorders	Polymyalgia rheumatic, tendonitis
Immune system disorders	Sarcoidosis
Infections and infestations	Encephalitis
	Pneumonia

17.10. Embryofoetal toxicity

Based on its mechanism of action, pembrolizumab can cause foetal harm if administered to a pregnant woman. Patients who are pregnant or breastfeeding are excluded from entering the trial. To be eligible for the trial, female and male patients of reproductive potential must be willing to use an adequate method of contraception for the first year of the trial and, if allocated to pembrolizumab, for the duration of treatment through to 120 days after the last dose of pembrolizumab (see appendix 2).

If a trial patient or a trial participants' partner becomes pregnant while receiving pembrolizumab, treatment should be permanently discontinued immediately. All pregnancies during treatment or up to 120 days after receiving pembrolizumab, should be reported to ICR-CTSU immediately using the pregnancy reporting form (see section 18.8).

17.11. Concomitant therapy and non-permissible medications

Medications or vaccinations specifically prohibited in the exclusion criteria (sections 5.4.2 and 9.2.2) and below are not allowed during the administration of pembrolizumab treatment. If there is a clinical indication for any medication or vaccination specifically prohibited during the trial, discontinuation from pembrolizumab may be required and this should be discussed with the Chief Investigator (or designated TMG member). The decision to continue the patient on trial therapy requires the mutual agreement of the Chief Investigator (or designated TMG member, if the Chief Investigator is unavailable), Principal Investigator (or designated investigator) and the patient.

17.11.1. Acceptable concomitant medications

All treatments that the investigator considers necessary for a patient's welfare may be administered at the discretion of the investigator in keeping with the community standards of medical care. All concomitant medication will be recorded on the eCRF including all prescription, over-the-counter (OTC), and IV medications and fluids.

All concomitant medications received within 28 days before commencing treatment with pembrolizumab and 30 days after the last dose of pembrolizumab should be recorded.

17.11.2. **Prohibited concomitant medications**

Patients are prohibited from receiving the following therapies:

- Antineoplastic systemic chemotherapy or biological therapy
- Immunotherapy not specified in this protocol
- Investigational agents other than pembrolizumab
- Radiation therapy (except planned loco regional adjuvant radiotherapy)
- Live vaccines within 30 days prior to commencing pembrolizumab and during pembrolizumab treatment. Examples of live vaccines include, but are not limited to, the following: measles, mumps, rubella, varicella, herpes zoster, yellow fever, rabies, BCG, and typhoid (oral) vaccines. Seasonal influenza vaccines for injection are generally killed virus vaccines and are allowed. However, intranasal influenza vaccines are live attenuated vaccines, and are not allowed.
- After commencing pembrolizumab: Glucocorticoids for any purpose other than to modulate symptoms from an event of clinical interest of suspected immunologic etiology. The use of physiologic doses of corticosteroids may be approved after consultation with the Chief Investigator (or designated TMG member).

Patients who, in the assessment by the investigator, require the use of any of the aforementioned treatments for clinical management may need to be discontinued from trial treatment (see section 17.11). Patients may receive other medications that the investigator deems to be medically necessary.

17.12. Dose modifications

AEs (both non-serious and serious) associated with pembrolizumab exposure may represent an immunologic aetiology. These AEs may occur shortly after the start of treatment or several months after the last dose of treatment. Pembrolizumab should be withheld for drug-related toxicities, and severe or life-threatening AEs, as per section 17.16 below. Supportive care guidelines, including use of corticosteroids, is also found in section 17.16.

17.13. Missed doses

Dosing interruptions are permitted in the case of medical/surgical events or logistical reasons not related to trial therapy (e.g. elective surgery, unrelated medical events, patient vacation, and/or holidays). Patients should be placed back on pembrolizumab treatment within 3 weeks of the scheduled interruption, unless discussed and agreed otherwise with the Sponsor. The reason for interruption of pembrolizumab treatment should be documented in the patient's trial record.

17.14. Overdoses

For this trial, an overdose will be defined as \geq 1000 mg (5 times the dose) of pembrolizumab. No specific information is available on the treatment of overdose of pembrolizumab. In the event of overdose, the patient should be observed closely for signs of toxicity. Appropriate supportive treatment should be provided if clinically indicated. Following investigations into the cause and effect of the overdose, the patient may continue on trial treatment if effects are minor and the patient and treating clinician agree to continue with pembrolizumab treatment.

If an adverse event(s) is associated with ('results from') the overdose of pembrolizumab, the adverse event(s) should be reported as a serious adverse event, even if no other seriousness criteria are met.

If a dose of pembrolizumab meeting the protocol definition of overdose is taken without any associated

clinical symptoms or abnormal laboratory results, the overdose should be reported as a non-serious Event of Clinical Interest (ECI), using the terminology "accidental or intentional overdose without adverse effect."

All reports of overdose with and without an adverse event must be reported within 24 hours to the ICR-CTSU (see section 18.1.5.).

17.15. Discontinuation and subsequent therapy

In cases where toxicity does not resolve to grade 0-1 within 12 weeks after the last infusion, pembrolizumab should be discontinued. Patients with a laboratory adverse event still at grade 2 after 12 weeks post last infusion may restart pembrolizumab if asymptomatic and only after consultation with the Chief Investigator.

17.16. Pembrolizumab Dose Modification Guidelines for Drug-Related AE

General instructions:

- 1. Corticosteroid taper should be initiated upon AE improving to Grade 1 or less and continue to taper over at least 4 weeks.
- 2. For situations where pembrolizumab has been withheld, pembrolizumab can be resumed if AE has been reduced to Grade 1 or 0 and corticosteroid has been appropriately tapered to <10mg prednisolone (or equivalent) per day within 12 weeks of the last pembrolizumab infusion. Pembrolizumab should be permanently discontinued if AE does not resolve within 12 weeks of last dose or corticosteroids cannot be reduced to ≤10 mg prednisone or equivalent per day within 12 weeks.
- 3. Patients with a laboratory adverse event still at grade 2 after 12 weeks post last infusion may restart pembrolizumab if asymptomatic and only after consultation with the chief investigator.
- 4. For severe and life-threatening Immune Related AEs, IV corticosteroid should be initiated first followed by oral steroid. Other immunosuppressive treatment should be initiated if irAEs cannot be controlled by corticosteroids.

Immune-related AEs	Toxicity grade or conditions (CTCAE v4.0)	Action taken to pembrolizumab	Immune related AE management with corticosteroid and/or other therapies	Monitor and follow-up
Pneumonitis	Grade 2 Grade 3 or 4, or	Withhold Permanently	 Administer corticosteroids (initial dose of 1-2 mg/kg/day prednisone or equivalent) Administer additional anti-inflammatory managements as product 	 Monitor participants for signs and symptoms of pneumonitis Evaluate participants with suspected pneumonitis with radiographic imaging and initiate corticosteroid treatment
	recurrent Grade 2	discontinue	 inflammatory measures as needed. Add prophylactic antibiotics for opportunistic infections 	
Diarrhea / Colitis	Grade 2 (for > 3 days) or 3	Withhold	 Administer corticosteroids (initial dose of 1-2 mg/kg/day prednisone or equivalent) 	 Monitor participants for signs and symptoms of enterocolitis (i.e. diarrhoea, abdominal pain, blood or mucus in stool with or without fever) and of bowel perforation (i.e. peritoneal signs and ileus). Participants with ≥ Grade 2 diarrhea suspecting colitis should consider GI consultation and
	Grade 4	Permanently discontinue		 performing endoscopy to rule out colitis. Participants with diarrhea/colitis should be advised to drink liberal quantities of clear fluids. If sufficient oral fluid intake is not feasible, fluid and electrolytes should be substituted via IV infusion
AST / ALT elevation or Increased bilirubin	Grade 2	Withhold	 Administer corticosteroids (initial dose of 0.5- 1 mg/kg/day prednisone or equivalent) 	 Monitor with liver function tests (consider weekly or more frequently) until liver enzyme value returned to baseline or is stable

ICR-CTSU

	Grade 3 or 4	Permanently discontinue	 Administer corticosteroids (initial dose of 1-2 mg/kg/day prednisone or equivalent) 	
Type 1 diabetes mellitus (T1DM) or Hyperglycemia	Newly onset T1DM or Grade 3 or 4 hyperglycemia associated with evidence of β-cell failure	Withhold until patient is clinically and metabolically stable	 Initiate insulin replacement therapy for participants with T1DM and for grade 3- 4 hyperglycemia associated with metabolic acidosis or ketonuria Administer anti-hyperglycemic in participants with hyperglycemia 	 Monitor participants for hyperglycemia or other signs and symptoms of diabetes. Evaluate patients with serum glucose and a metabolic panel, urine ketones, glycosylated hemoglobin, and C-peptide. For patients with grade 3 or 4 endocrinopathy that improves to grade 2 or less and is controlled with hormone replacement, continuation of pembrolizumab may be considered.
Hypophysitis	Grade 2	Withhold	 Administer corticosteroids and initiate hormonal replacements as clinically indicated. 	 Monitor for signs and symptoms of hypophysitis (including hypopituitarism and adrenal insufficiency)
	Grade 3 or 4	Withhold or permanently discontinue ^a	Therapy with pembrolizumab can be continued while endocrine replacement therapy is instituted	 Replacement of appropriate hormones may be required as the corticosteroid dose is tapered. For patients with grade 3 or 4 endocrinopathy that improves to grade 2 or less and is controlled with hormone replacement continuation of pembrolizumab may be considered.
Hyperthyroidism	Grade 3	Withhold	 Treat with non-selective beta-blockers (e.g., propranolol) or thionamides as appropriate 	 Monitor for signs and symptoms of thyroid disorders. Any grade 2 hyperthyroidism may also be treated
	Grade 4	Discontinue ^a	 Replacement of appropriate hormones may be required as the corticosteroid dose is tapered. 	 Any grade 2 hyperthyroidism may also be treated as recommended. For patients with grade 3 or 4 endocrinopathy that improves to grade 2 or less and is controlled with hormone replacement continuation of pembrolizumab may be considered.
Hypothyroidism	Grade 2-4	Continue	 Initiate thyroid replacement hormones (e.g. levothyroxine or liothyroinine) per standard of care 	 Monitor for signs and symptoms of thyroid disorders. For patients with grade 3 or 4 endocrinopathy that improves to grade 2 or less and is controlled with hormone replacement continuation of pembrolizumab may be considered.
	Grade 2	Withhold		Monitor changes of renal function

ICR-CTSU

Nephritis ^b and Renal dysfunction	Grade 3 or 4	Permanently discontinue	Administer corticosteroids (prednisone 1-2 mg/kg/day or equivalent)	
Myocarditis	Grade 1 or 2	Withhold	Based on severity of AE administer corticosteroids	Ensure adequate evaluation to confirm etiology and/or exclude other causes
	Grade 3 or 4	Permanently discontinue		
	Grade 2	Withhold		Permanently discontinue if toxicity develops despite adequate premedication
Infusion Reaction ^c	Grade 3 or 4	Permanently discontinue		
Hepatitis	Grade 2 - 4	Withhold	 For grade 2, administer corticosteroids (prednisone 0.5-1mg/kg/day or equivalent) For grade 3 / 4, administer corticosteroids (prednisone 1-2 mg/kg/day or equivalent) 	Withhold or discontinue pembrolizumab based on severity of liver enzyme elevations.
Skin reactions including:	Grade 2 or 3	Withhold	 Administer corticosteroids (prednisone 1-2 mg/kg/day or equivalent) 	 Monitor patients for suspected severe skin reactions and exclude other causes.
 Dermatitis exfoliative Erythema multiform Exfoliative rash Bullous pemphigoid Stevens-Johnson syndrome grade ≥ 3 pruritus and rash (generalised or maculopapula r) 	Grade 4	Permanent discontinue		 Refer the patient to dermatology for assessment and treatment. If SJS or TEN is confirmed, permanently discontinue pembrolizumab.
All other immune- related AEs ^d	Intolerable/ persistent Grade 2	Withhold	 Based on type and severity of AE administer corticosteroids 	 Ensure adequate evaluation to confirm etiology and/or exclude other causes
May include:	Grade 3	Withhold or discontinue based on		• Pembrolizumab may only be restarted after grade 3 reactions following discussion with the ICR-CTSU.

|--|--|

Note: Permanently discontinue pembrolizumab for any severe or grade 3 (grade 2 for pneumonitis) drug-related AE that recurs or any life-threatening event.

- a. Withholding or permanently discontinuing pembrolizumab is at the discretion of the investigator or treating physician.
- b. Renal function can be calculated using Serum creatinine OR estimated GFR (using Cockcroft-Gault).

c. For infusion reactions: if symptoms resolve within one hour of stopping drug infusion, the infusion may be restarted at 50% of the original infusion rate (e.g., from 100 mL/hr to 50 mL/hr). Otherwise dosing will be held until symptoms resolve and the patient should be pre-medicated for the next scheduled dose; Refer to Table 2 – Infusion Treatment Guidelines for further management details.

d. Patients with intolerable or persistent grade 2 drug-related AE may hold pembrolizumab at investigator's discretion. Permanently discontinue pembrolizumab for persistent grade 2 adverse reactions for which pembrolizumab has been on hold for ≥12 weeks.

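### Section 17.16, hypophysitis: the management text allows pembrolizumab to continue while hormone replacement is started, but the action cells offer only withholding or stopping, and nothing says which governs

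*Protocol*

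**What the plan says.** The dose modification table in Protocol section 17.16 gives each immune-related event an action column, a management column and a follow-up column. For hypophysitis:

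- **Action, grade 2:** "Hypophysitis Grade 2 Withhold". No footnote is attached.
- **Action, grade 3 or 4:** "Withhold or permanently discontinue", with footnote a, which reads "Withholding or permanently discontinuing pembrolizumab is at the discretion of the investigator or treating physician".
- **Management:** "Administer corticosteroids and initiate hormonal replacements as clinically indicated", followed by "Therapy with pembrolizumab can be continued while endocrine replacement therapy is instituted". In the running text of the table, the second sentence falls on the grade 3 or 4 line.
- **Follow-up:** a standing sentence for patients with a grade 3 or 4 "endocrinopathy that improves to grade 2 or less and is controlled with hormone replacement, continuation of pembrolizumab may be considered". The wording quoted is that of the diabetes row. The hypophysitis, hyperthyroidism and hypothyroidism rows repeat it, apart from a comma.

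Three other places bear on the row. Section 17.12 says "Pembrolizumab should be withheld for drug-related toxicities, and severe or life-threatening AEs, as per section 17.16 below". General instruction 2 at the head of section 17.16 allows a withheld patient to resume once the event is at grade 0 or 1 and the corticosteroid has been tapered. Section 17.6 likewise ties restarting to grade 1 or less.

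**The concern.** No action cell for hypophysitis offers continuing, yet the management text of the same row permits it. Two sites could each follow the row faithfully and do opposite things for the same immune-mediated event, one interrupting treatment and the other carrying on while replacement is started. That is first a matter of patient safety.

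It also touches reporting to a small degree. Section 19.3.2 includes the proportion of patients with a dose reduction or delay under safety and tolerability, and for a hypophysitis case that entry could depend on which cell the site followed.

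**Working it through.** The main check is a comparison of texts. The protocol states no figure on this point that could be reproduced.

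**Step 1: action against management.** The action cells allow withholding (grade 2) and withholding or permanent discontinuation (grade 3 or 4). The management sentence allows continuing. It names no grade, does not require a prior hold, and does not require recovery. Its timing is the period when replacement is being started.

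**Step 2: which grades are affected.** There are two possible layouts.

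- If the sentence belongs to the grade 3 or 4 line, as printed, it stands against the grade 3 or 4 action cell.
- If the management cell is merged over both grades, it also stands against the grade 2 action cell, where no footnote gives discretion.

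The text alone does not settle the layout. In either case the sentence faces an action cell without a continue option.

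**Step 3: footnote a.** It is attached at grade 3 or 4 only and can be read in two ways.

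- As a choice between withholding and stopping, which is the plainer reading. The conflict then stands.
- As making any interruption optional. The conflict at grade 3 or 4 then softens, because a permissive sentence can sit beside an optional action.

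**Step 4: management against follow-up.** The follow-up cell lets continuation be considered after a grade 3 or 4 event has improved to grade 2 or less and is controlled with replacement. The management sentence carries neither condition, so a site relying on it bypasses both.

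**Step 5: follow-up against general instruction 2.** The follow-up threshold is grade 2 or less. General instruction 2 and section 17.6 require grade 1 or less. No text says whether the endocrine sentence overrides the general rule.

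**Step 6: does other text resolve it?** Section 17.12 refers the reader back to section 17.16. Other rows show that the table can be explicit: the hypothyroidism action cell says to continue at grades 2 to 4, and the diabetes action cell says to withhold until the patient is clinically and metabolically stable. The hypophysitis action cells take neither form.

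**Step 7: how often it could matter.** Inputs:

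- Rate of hypophysitis, all grades: 0.6% (section 1.2.3), assumed to apply to this trial.
- Numbers treated: 30 and 45, the pembrolizumab allocations at 30% and 45% ctDNA positivity in the section 19.1.2 table, which reflect the former 2:1 randomisation. Also 68, all ctDNA-positive patients at 45% positivity, taken as if every one started treatment.

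Chance of at least one case = 1 − (1 − 0.006)^n; expected cases = 0.006 × n.

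| n | Chance of at least one case | Expected cases |
|---|---|---|
| 30 | 1 − 0.994^30 = 16.5% | 0.18 |
| 45 | 1 − 0.994^45 = 23.7% | 0.27 |
| 68 | 1 − 0.994^68 = 33.6% | 0.41 |

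The 0.6% includes grade 1, for which the row has no action line, so at this rate each figure overstates how often the conflicting cells would be met.

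**The case against.** The best defence has four parts.

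- **Layout.** The sentence is printed on the grade 3 or 4 line, so a reader who infers that a grade 2 patient is plainly told both to withhold and to continue goes further than the text allows. This stands: the grade 2 conflict depends on the management cell covering both grades.
- **Footnote a.** It may make interruption discretionary at grade 3 or 4, in which case the row does not order a hold there. This stands as a possible reading. It shows that the row needs clarifying and does not show that the row is clear.
- **The follow-up cell.** A reader might infer that it contradicts the grade 2 hold, since it lets a patient at grade 2 continue. The document does not support that. The grade 2 line concerns the initial response to a grade 2 event. The follow-up sentence concerns a later state, a grade 3 or 4 event that has improved and is controlled, and it recurs across the endocrine rows as a standing conditional rule. An initial hold and a later conditional continuation can both apply. What remains is the mismatch with general instruction 2.
- **Meaning of continued.** The sentence may have been intended as resuming after a hold. The cell does not say so, and the timing it gives is while replacement is being started, not after recovery.

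It is also fair to say that most likely no patient will be affected, and that no calculation for a primary endpoint depends on this row.

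**Conclusion.** The inconsistency is real but narrower than it may first appear. As printed, the management sentence conflicts with the grade 3 or 4 action cell. The conflict extends to grade 2 only if the management cell spans both grades, and it softens at grade 3 or 4 if footnote a makes interruption optional. The sentence also bypasses the follow-up cell's conditions, and the follow-up threshold differs from general instruction 2 with no order of precedence given.

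The size is small: fewer than one expected case, with about a 17% to 34% chance of at least one among 30 to 68 treated patients, assuming the protocol's 0.6% all-grade rate applies. A reader might take the figure for 45 patients (24%) as a ceiling. It is not one, because 30 and 45 come from the superseded 2:1 allocation, and section 19.1.2 says that closing randomisation may raise the number treated. Nor do these numbers support a claim that exposure or withholding rates would be materially distorted. The reason to act is that a safety table should not give a treating team two answers.

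**What to change.** Reconcile the action, management and follow-up cells of the hypophysitis row with footnote a and general instruction 2, so that each grade carries one instruction. In particular:

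- State the grade or grades to which the management sentence applies, and whether it presupposes a hold.
- State whether footnote a is a choice between withholding and stopping or makes interruption itself optional.
- State which text governs while replacement is being started, and which governs after improvement, where the endocrine follow-up sentence and general instruction 2 set different thresholds.

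Which clinical rule is right is for the sponsor's clinicians. The cost is table wording in the next amendment; no patients, visits or procedures are added.
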